11.3 ROUTINE CLOSE-OUT

Routine close-out activities will be conducted to ensure that the Investigator's records are complete, all documents needed for the Sponsor's files are retrieved, remaining clinical investigation materials are disposed of, previously identified issues have been resolved, and all parties are notified.

12. PROTOCOL DEVIATIONS

A protocol deviation is an event whereby the clinical Investigator or site personnel did not conduct the study according to the protocol. Conformance to the protocol is essential to the quality and integrity of the clinical study. Every effort should be made to avoid any deviation from the clinical protocol.

Under emergency circumstances, deviations from the protocol to protect the rights, safety and well-being of human subjects may proceed without prior approval of the Sponsor and the IRB. Such deviations shall be documented and reported to the Sponsor within 5 days of knowledge. The IRB should be notified of the deviation as required by IRB reporting guidance.

The Sponsor is responsible to assess protocol deviations in an ongoing manner and determine their impact on the conduct of the study. After evaluation of each deviation, the Sponsor will determine if corrective and preventive actions need to occur.

The Sponsor reserves the right to disqualify Investigator on the basis of repeated or serious deviations at their site.

13. CONCOMITANT MEDICATIONS

For the purposes of this clinical study, only current medications being taken or administered for the following will be recorded:

- Pain (any type);
- Inflammation (any type);
- Muscle relaxation;
- Numbness and/or tingling;
- Hormonal replacement therapy; and
- Medications prescribed for treatment of AEs/SAEs

14. ADVERSE EVENT AND DEVICE DEFICIENCY REPORTING

14.1 DEFINITIONS

Device Deficiency (DD) - A device deficiency is an inadequacy of a medical device with respect to its identity, quality, durability, reliability, safety or performance. Device deficiencies include malfunctions, use errors, and inadequate labelling.

Adverse Event (AE) – An adverse event is any untoward medical occurrence, disease, injury, or untoward clinical signs (including abnormal laboratory findings, surgical complications, etc.), whether related or unrelated to the investigational device or its use.

Serious Adverse Event (SAE) – A Serious Adverse Event is an AE which:

1. Led to a death,
2. Led to serious deterioration in the health of the subject that either resulted in:
 - a) A life-threatening illness or injury, or
 - b) A permanent impairment of a body structure or a body function, or
 - c) In-patient hospitalization or prolonged hospitalization, or
 - d) Medical or surgical intervention to prevent life threatening illness or injury or permanent impairment to a body structure or a body function.
3. Led to fetal distress, fetal death or a congenital abnormality or birth defect (not anticipated in this study as pregnant women are excluded from the study).
4. Other Serious (Important Medical Events)

NOTE: Planned hospitalization including for any pre-existing condition, without a serious deterioration in health, is not considered a serious adverse event.

Unanticipated Adverse Device Effect (UADE) – An Unanticipated Adverse Device Effect is:

- Any serious adverse effect on health or safety or any life threatening problem or death caused by, or associated with, a device, if that effect, problem, or death is not previously identified in nature, severity, or degree of incidence in the IDE application; or
- Any other unanticipated serious problem associated with a device that relates to the rights, safety, or welfare of the subjects.

14.2 CLASSIFICATION OF AN AE

14.2.1 Severity

The Investigator will assess the severity of the AE and classify it according to the following definitions:

MILD: Event/symptom is transient and well-tolerated by the subject.

MODERATE: Event/symptom causes discomfort and interferes with routine activities of the subject.

SEVERE: Event/symptom interferes considerably with the routine activities of the subject or causes inability to work.

These definitions are for descriptive purposes only and are independent of the judgment of whether an event is classified as an AE or an SAE.

14.2.2 Relationship

The relationship between the use of the medical device (including the medical procedure) and the occurrence of each adverse event shall be assessed and categorized. During causality assessment, clinical judgment shall be used, and the Clinical Protocol shall be consulted, as all the foreseeable potential risks are listed here. The presence of confounding factors, such as concomitant medication/treatment, other concurrent illness or risk factors shall also be considered.

The Investigator will assess the potential relationship of the AE or SAE to the use of the investigational device/procedure and classify the causality of the event according to the following definitions.

Clinical Study Protocol

DEFINITELY RELATED: An AE that has a strong causal relationship. An AE that follows a strong temporal relationship, follows a known response pattern, and cannot reasonably be explained by known characteristics of the subject's clinical state or other therapies.

PROBABLY RELATED: An AE that potentially has a causal relationship. The AE has a reasonable temporal relationship and alternative etiology is less likely compared to the potential relationship to the use of the investigational device/procedure.

POSSIBLY RELATED: An AE that potentially has a causal relationship. The AE has a reasonable temporal relationship to the use of the investigational device/procedure but alternative etiology is equally likely compared to the potential relationship to the use of the investigational device/procedure.

NOT RELATED: An AE without any apparent causal relationship. The AE is due to the underlying disease state or is due to concomitant medication or therapy not related to the use of the investigational device/procedure.

UNKNOWN RELATIONSHIP: If the AE cannot be determined to have a causal relationship, it will be classified as unknown.

NOTE: Where the Investigator or Sponsor remains uncertain about how to classify the event, this should not cause them to exclude any possible relatedness, and the Investigator should consider classifying the event as "Possibly Related".

14.3 AE REPORTING PROCEDURES

14.3.1 AE Reporting

An AE is any undesirable clinical occurrence in a subject (including abnormal laboratory findings) whether or not it is related to the investigational device. Any condition at baseline that is recorded as a preexisting condition is not an AE unless it worsens in intensity or duration.

The collection of AEs will begin in the exam room once the patient is enrolled, i.e. the Investigator delivers the local anesthetic. All AEs that occur through completion of the final follow-up visit for each subject (day 30), whether observed by the Investigator or by the subject, and whether or not thought to be device-related, should be reported in detail and followed to resolution.

The description of the AE will include the date and time of onset, severity, causal relationship to the investigational device, if any treatment was required, and the outcome of the event. Significant new information and updates should continue to be captured in the subject's records and in the EDC as they become available and the adverse event should be followed until it is resolved or no further improvement is expected, or the subject is lost to follow-up.

14.3.2 SAE Reporting

Using the contact information below, the Sponsor should be notified of all SAEs within one (1) business day of the site becoming aware of the event by entering SAE information in the EDC. In the event the EDC is unavailable for any reason, notification to Active Life should be made via email or phone as follows:

Sponsor Contact: [name]
E-mail: [contact]
[contact] x106

Clinical Study Protocol

The Investigator will provide additional information on the SAE by updating the information in the EDC as updates become available. The Sponsor may also ask for additional clinical reports including redacted source documents to be provided by the Investigator to assist in the assessment of the event. Significant new information and updates should continue to be submitted promptly to the Sponsor and entered in the EDC as they become available, and the adverse event should be followed until it is resolved or no further improvement is expected, or the subject is lost to follow-up.

The Sponsor shall ensure that the Investigator submits safety event notifications to the governing IRB within the timeframe specified by the IRB, when applicable. Acceptable means of confirming that the IRB requirements have been met include forwarding a copy of the written, signed report that was sent to the IRB to the Sponsor. Copies of this report should be filed in the Investigator's site files and the Sponsor's Trial Master File.

New SAEs will only be documented for each subject until the last study related subject visit (day 30).

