1.1 SCHEDULE OF EVENTS

Activity	Visit 1 Screening/ Procedure ¹	Visit 2 1-Day ^{2,3} (+ 2 days)	Visit 3 7-Day ^{2,3} (±3 days)	Visit 4 30-Day ² (±10 days)	Unscheduled
Informed Consent	X	-	-	-	-
Inclusion/Exclusion Criteria Review	X	-	-	-	-
Demographics	X	-	-	-	-
Medical History	X	-	-	-	-
Physical Examination (including vitals)	X	-	-	-	-
X-Rays (AP & Lateral)	X	-	-	-	-
Pregnancy Evaluation/Test ⁴	X	-	-	-	-
OsteoProbe Test Procedure	X	-	-	-	-
NRS Pain Score	X ⁵	X	X	X	X
Record BMSi Score	X	-	-	-	-
Body Temperature		X	X	X	X
Record/Review Concomitant Medications	X	X	X	X	X
Record/Review Adverse Events	X ⁶	X ⁶	X ⁶	X ⁶	X ⁶
Record/Review Device Deficiencies	X	-	-	-	-
Work status	X	X	X	X	X

¹ The Screening/Procedure visit may take place over multiple days, but the OsteoProbe procedure must be completed within 7 days of signing the ICF.

² To be conducted as telehealth visits with video interviews; option of in-person visits is acceptable if that is preferred by a subject or the Investigator.

³ Measured from the date of the OsteoProbe procedure.

⁴ Female subjects of child-bearing potential only. Negative pregnancy status can be based on self-reported sexual history and contraception use. An in-clinic test must be performed using urine dipstick when the subject thinks there is a potential that they might be pregnant.

⁵ The NRS Survey must be completed once prior to the OsteoProbe procedure (baseline) and again following completion of the procedure.

⁶ X-rays will be ordered by the Investigator to evaluate any adverse event that may be related to a potential tibial fracture based on clinical exam and/or adverse event details provided by the subject.

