7.10 SUBJECT ENROLLMENT

The point of enrollment occurs when the Investigator delivers the local anesthetic. All enrolled subjects, including those found to be ineligible after consent, will be followed for the next 30 days in accordance with the Schedule of Assessments.

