7.11 TREATED SUBJECTS

A treated subject is an enrolled subject who has had the OsteoProbe measurement procedure completed and a BMSi measurement was recorded. All treated subjects, including those found to be ineligible after enrollment, will be followed for the next 30 days in accordance with the Schedule of Assessments.

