8.5 OUT OF WINDOW AND MISSED VISITS

If a subject fails to participate in a scheduled study visit within the visit window defined in the study protocol but completes the visit prior to the beginning of the next visit window, that visit is considered to have been completed out of window. A protocol deviation must be documented on the appropriate eCRF.

If a subject fails to participate in a scheduled study visit within the visit window defined in the study protocol and the next scheduled study visit window opens, that visit is considered to have been missed. A protocol deviation should be documented on the appropriate eCRF.

All attempts should be made to schedule the subject for the study follow-up as soon as possible so that it is captured late rather than missed completely.

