8.7 STUDY COMPLETION/DISCONTINUATION

The Primary Endpoints will be evaluated after all subjects reach their 30-Day follow-up visit. Subjects will complete study participation after their 30-Day follow-up visit.

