18. STATISTICAL ANALYSIS PLAN

18.1 STUDY HYPOTHESIS

The primary hypothesis is that the probability of experiencing device-related Serious Adverse Events (SAE) for subjects treated with the investigational device is smaller than the performance goal of 1%. Formally, that hypothesis to be tested are:

H_0 : The expected proportion of subjects with device-related SAE up to Day 30 (p_T) is greater than or equal to the performance goal (PG) of 1.0%.

H_A : The expected proportion of subjects with device-related SAE up to Day 30 (p_T) is less than the performance goal (PG) of 1.0%.

These hypotheses may be symbolically represented as:

$$H_0: p_T \geq PG = 1.0\%$$

$$H_A: p_T < PG = 1.0\%$$

Where p_T is the device-related SAE rate for subjects treated with the investigational device.

If the Bayesian Posterior Probability that $p_T < PG$ is greater than or equal to .975, the alternative hypothesis will be accepted, and it will be concluded that the device meets the performance goal.

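### The primary hypothesis covers device-related SAEs up to Day 30, but SAE documentation ends at a final visit allowed from Day 20 to Day 40, so the endpoint period and the observation period do not match

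*Combined protocol and SAP*

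**What the plan says.** - **Endpoint period.** The null and alternative hypotheses in section 18.1 (repeated in the Study Summary) are about "The expected proportion of subjects with device-related SAE up to Day 30". Section 6.3, which defines the primary endpoint, gives no time limit. Section 6.4 defines the secondary safety endpoints through Day 30.
- **Observation period.** Section 14.3.1 collects "All AEs that occur through completion of the final follow-up visit for each subject (day 30"), and section 14.3.2 says "New SAEs will only be documented for each subject until the last study related subject visit (day 30"). Section 8.7 adds: "Subjects will complete study participation after their 30-Day follow-up visit".
- **Visit window.** The Study Summary, the Schedule of Events (1.1) and section 8.4 all allow the 30-day visit at ±10 days.
- **Anchor.** Footnote 3 of the Schedule of Events, "Measured from the date of the OsteoProbe procedure", is attached to Visits 2 and 3 but not to Visit 4.
- **Follow-up promise.** Section 7.10 says enrolled subjects "will be followed for the next 30 days in accordance with the Schedule of Assessments". Section 7.11 makes the same promise for treated subjects: "All treated subjects, including those found to be ineligible after enrollment, will be followed for the next 30 days", again tied to that schedule.
- **Status of an early visit.** Under section 8.5 a visit is out of window or missed only if the subject "fails to participate in a scheduled study visit within the visit window defined in the study protocol". Under section 10.1 only a subject who misses the 30-day visit is lost to follow-up.
- **Prior data.** Section 18.2 admits a historical study only if its patients had at least 30 days of follow-up.

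**The concern.** The trial's only confirmatory claim is a 30-day rate, yet its procedures do not secure 30 days of observation in every compliant subject. A subject whose final visit falls on Days 20 to 29 has followed the protocol, has no deviation, is not lost to follow-up and stays in the Primary Analysis Set (18.3.1). Section 18.5 does not define this subject as missing. No section says how the subject is scored; counting a 30-day non-event is the natural reading.

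The gap concerns only SAEs with new onset between the visit and Day 30, because events already open are followed further (6.1, 14.3.1, 14.3.2). Later SAEs would come to light only if volunteered, since no contact is scheduled after the final visit and unscheduled visits are made as needed (8.6).

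Two things raise the stakes. The decision rule tolerates no event at all (18.2, 18.4), and the prospective subjects are pooled with historical subjects who had to meet a 30-day minimum. The secondary safety endpoints in 6.4 have the same gap.

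**Working it through.** **1. The plan's own figure.** Inputs from 18.1 and 18.2: Jeffreys prior Beta(0.5, 0.5), 0 events in 215 prior subjects, 40 prospective subjects, goal 1%, threshold .975. With x events among N subjects in total, the posterior probability is the Beta(0.5 + x, 0.5 + N − x) distribution function at 0.01.

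| Prior subjects | N | x = 0 | x = 1 |
|---|---|---|---|
| 215 | 255 | 0.97649 | 0.83683 |
| 270 (Table 8, anticipated) | 310 | 0.98748 | 0.89889 |

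The stated .9765 is reproduced. One event fails under either prior.

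**2. The window.** Counted from the procedure, the earliest compliant final visit is 30 − 10 = Day 20 and the latest is 30 + 10 = Day 40. The largest unobserved stretch is 30 − 20 = 10 days, one third of the endpoint period.

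**3. Effect on the chance of passing, counting only onset by Day 30.** Let p be the true 30-day rate and f the average share of the 30-day risk that is observed. Then P(0/40) = (1 − f·p)^40. The documents give neither visit timing nor onset times, so each f is an assumption:

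- Even spread over Days 20–40: half the visits fall before Day 30, and these lose on average half of the last 10 days, so one quarter of the risk in Days 20–30 is lost. With constant hazard, f = 1 − (1/3)(1/4) = 0.9167. With 10% of the risk after Day 20, f = 1 − 0.1/4 = 0.975. In whole days, about 40 × 10/21 = 19 subjects would be last seen before Day 30.
- Every visit on Day 20: f = 2/3 with constant hazard; f = 0.9 with 10% of the risk after Day 20.

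| Assumption | f | p = 1% | p = 2% | p = 5% |
|---|---|---|---|---|
| Full 30 days | 1 | 66.9% | 44.6% | 12.9% |
| Even spread, 10% of risk after Day 20 | 0.975 | 67.6% | 45.5% | 13.6% |
| Even spread, constant hazard | 0.9167 | 69.2% | 47.7% | 15.3% |
| All on Day 20, 10% of risk after Day 20 | 0.9 | 69.7% | 48.4% | 15.9% |
| All on Day 20, constant hazard | 0.667 | 76.5% | 58.5% | 25.8% |

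**4. The same, counting every event documented up to the visit.** With an even spread and constant hazard, mean observation is (20 + 40)/2 = 30 days, so f = 1 and P(0/40) is 66.9%, 44.6% and 12.9%. There is no net change.

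**5. Treating early leavers as missing in the primary analysis (0 events, 215 prior).** Imputing from the posterior that includes the prior adds no information, so only observed subjects count: 215 + 35 = 250 gives 0.9751 (pass), and 215 + 34 = 249 gives 0.9748 (fail). Six imputed subjects therefore defeat the claim. If imputation uses trial data alone with a Jeffreys start, one such subject has event probability 0.5/40 = 0.0125, and 0.9875 × 0.97649 + 0.0125 × 0.83683 = 0.9747 (fail).

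**The case against.** Day 30 may be only the name of the visit. Sections 14.3.1 and 14.3.2 attach it to the final visit, and 8.7 evaluates the primary endpoint once all subjects reach that visit. On this reading the ±10 days is an ordinary symmetric window and nothing goes unobserved. The reading is possible, but the hypothesis is worded as a period ending on Day 30, sections 7.10 and 7.11 speak of 30 days, and the prior studies needed at least 30. Those two sections do not close the gap either, because they defer to the schedule that carries the window.

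A reader might infer that the mismatch always favours the device. The documents do not support this. Late visits collect events after Day 30 and 6.3 does not exclude them; step 4 shows that the two sides can cancel. The gap favours the alternative hypothesis only if events count by onset up to Day 30.

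A reader might also infer that early leavers must be imputed in the primary analysis. Section 18.5 does not say so. Step 5 shows that the price would be high, and it would discard 20 to 29 days of event-free observation.

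That one event reverses the result is a property of the zero-event rule, and says nothing about how often this window hides one. This objection stands. Some protection also exists: open events are followed, best- and worst-case analyses are planned (18.5), and the investigator's UADE reports (20.5, Table 9) have no visit cut-off. None of these looks for a new, anticipated SAE after an early final visit.

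**Conclusion.** The mismatch is in the text and should be corrected. Provided that Visit 4 is timed from the procedure, which the schedule does not say, a compliant subject can have up to 10 endpoint days without planned ascertainment; a subject seen late has up to 10 days of collection beyond the endpoint period.

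The expected effect is small. At a true 1% rate, counting onset by Day 30, the chance of passing rises by 0.7 to 2.3 percentage points with visits spread evenly, and by 2.8 to 9.6 points if every visit fell on Day 20. These are illustrations. The largest should not be read as an upper bound, since a hazard weighted towards the end of the period would exceed it, and nothing in the documents shows which case is likely. Nor do the documents show that SAEs will be missed or that the posterior calculation is wrong: .9765 stands if every subject is followed to Day 30.

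**What to change.** Reconcile the Study Summary, 1.1, 8.4, 14.3.1, 14.3.2 and 18.1:

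1. State in 1.1 the date from which Visit 4 is counted, and in 14.3.1 and 14.3.2 that new AEs and SAEs are documented through at least Day 30.
2. Make the last safety contact fall on or after Day 30, within the existing Day 40 limit. Alternatively, keep the window and add a brief SAE-only telehealth contact for subjects seen earlier.
3. State in 6.3 and 18.4 that primary events count by onset date up to Day 30. Without this rule the direction of any bias is undefined.
4. Report how many subjects were last contacted before Day 30 and cover them in the best- and worst-case analyses of 18.5. Do not make their imputation the primary analysis.

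The cost is protocol and SAP wording and slightly more scheduling, mostly by telehealth, with no added subjects. Moving the visit itself may leave a few more visits out of window or missed, and a subject who misses it becomes lost to follow-up under 10.1. The SAE-only contact avoids most of that.

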14.3.3 Unanticipated Adverse Device Effect Reporting

The Sponsor shall review all reported SAEs to evaluate whether they meet the criteria for an Unanticipated Adverse Device Effect. For AEs that are determined to be UADEs, the Sponsor will submit an expedited safety report to the FDA's Center for Devices and Radiological Health (CDRH). The expedited safety report will be submitted to the FDA and governing IRB as soon as possible and, in no event, later than **ten (10) business days** after this is determined.

If, following receipt and investigation of follow-up information regarding an AE that was previously determined not to be a UADE, the Sponsor determines that the event does meet the requirements for expedited reporting, the Sponsor will notify the FDA as soon as possible, but in no event later than **ten (10) business days** after this is determined.

14.3.4 Study Termination due to an Unanticipated Adverse Device Effect (UADE)

Active Life Scientific, Inc., in consultation with the Investigators, shall determine if the reported event presents an unreasonable risk to study subjects. If the event is determined to pose an unreasonable risk, the Sponsor may terminate the investigation, or the parts of the investigation presenting that risk, within 5 business days after Sponsor makes an "unreasonable risk" determination or within 15 business days after Active Life Scientific, Inc. first received notice.

